a On dosing days, assessments will be performed before dosing, unless noted otherwise.b Additional PK samples and safety assessments may also be performed at the discretion of the investigator. See [Section 9.1.1.4](#) for details.c Subjects will be discharged from the CRU on Day 16 after completion of the study visit assessments.d Weight will be measured with shoes off.e Standard 12-lead ECGs will be performed in the supine position after the subject has been at rest for at least 5 minutes. The ECG will be done before any other procedures that may affect heart rate, such as blood draws. On Days 1 and 9, ECGs will be collected before dosing and approximately 1, 3, 5, and 6 hours ( $\pm$  15 min) after dosing.f Vital signs will be performed after the subject has been at rest for at least 5 minutes.g Blood samples for PK assessments will be collected on Days 1 and 9 before dosing (0 hours), and at 1, 1.5, 2, 3, 4, 5, 6, 8, 12, 24 (Days 2, 10), 36 (Days 2, 10), 48 (Days 3, 11), 72 (Days 4, 12), 96 (Days 5, 13), 120 (Days 6, 14), 144 (Days 7, 15), and 168 (Days 8, 16) hours after dosing. Acceptable PK sampling windows are provided in [Table 11-1](#). At the Safety Follow-up Visit, a single blood sample for PK analysis will be collected.h Subjects will be randomized 3:1 to receive VX-121 or placebo. Study drug will be administered in the fed state ([Section 9.6.1](#)).i All subjects will receive open-label VX-121. Study drug will be administered in the fed state and with milk ([Section 9.6.1](#)).j All medications taken from 28 days before the first dose of study drug through the end of the study will be recorded.

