**Table 3-4 Study VX17-121-001: Part A, Cohort A9, Treatment Period and Safety Follow-up Visit**

Event/Assessment a	Study Day										Safety Follow-up (7 to 10 Days After Last Dose of Study Drug) b
	-1	1	2	3,4,5, 6,7,8	9	10	11,12,13, 14,15,16	17	18	19,20,21, 22,23,24	
Inpatient days	X	X	X	X	X	X	X	X	X	X c	
Outpatient visit											X
Weight d	X										
Standard 12-lead ECG e	X	X			X			X			X
Vital signs f	X	X	X	X	X	X	X	X	X		X
Full physical examination	X										X
Serum chemistry	X		X			X			X		X
Hematology	X		X			X			X		X
Blood for PK analysis g		X	X	X	X	X	X	X	X		X
Drug test (urine or blood), including cotinine	X										
Alcohol test (urine, blood, or breath)	X										
Urinalysis											X
Study drug administration h			X		X			X			
Adverse events	Continuous from signing of ICF through Safety Follow-up Visit										
Medications review i	Continuous from signing of ICF through Safety Follow-up Visit										
Treatment and procedures review	Continuous from signing of ICF through Safety Follow-up Visit										

a On dosing days, assessments will be performed before dosing, unless noted otherwise.

b Additional PK samples and safety assessments may also be performed at the discretion of the investigator. See [Section 9.1.1.4](#) for details.

c Subjects will be discharged from the CRU on Day 24 after completion of the study visit assessments.

d Weight will be measured with shoes off.

e Standard 12-lead ECGs will be performed in the supine position after the subject has been at rest for at least 5 minutes. The ECG will be done before any other procedures that may affect heart rate, such as blood draws. On Days 1, 9, and 17, ECGs will be collected before dosing and approximately 1, 3, 5, and 6 hours ( $\pm$  15 min) after dosing.

f Vital signs will be performed after the subject has been at rest for at least 5 minutes.

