#### **9.1.1.2 Treatment Period**

Subjects will be admitted on Day -1 and will remain in the clinical research unit (CRU) for the duration of the Treatment Period.

Treatment Period assessments are listed in [Table 3-2](#) (Cohorts A1 through A6 [up to A8]), [Table 3-3](#) (Cohort A3), [Table 3-4](#) (Cohort A9), [Table 3-5](#) (Part B), and [Table 3-6](#) (Part C).

The treatment periods for Part A, B, and C will be conducted as described in [Section 9.1.1](#). Dosing details are given in [Section 9.6.1](#).

If a subject has any clinically significant, study-related abnormalities at the conclusion of a scheduled inpatient portion of the study, the medical monitor (or authorized designee) will be notified, and the subject will be asked to remain in the CRU until such abnormalities resolve. If the subject is unable or unwilling to remain in the CRU, the medical monitor (or authorized designee) will be notified, and the investigator will make every effort to arrange follow-up evaluations at appropriate intervals to document the course of the abnormalities.

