#### **12.3.4 Safety Analysis**

Safety is the primary objective of this study. The overall safety profile of VX-121 will be assessed in terms of the following primary (safety) endpoints:

- Incidence of treatment-emergent adverse events (TEAEs)
- Clinical laboratory values (including coagulation studies)
- ECG outcomes

- Vital signs
- Spirometry (Part D only)

Safety analyses will be based on the Safety Set. No statistical hypothesis testing will be conducted.

For safety variables, the baseline value will be defined as the most recent non-missing measurement collected before the initial administration of study drug.

All safety data will be presented in individual subject data listings.

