- **TE Period 2 (tablet [fed])** will begin from administration of VX-121 tablet in the fed state (1) until the administration of VX-121 tablet in the fed state and with milk, or (2) the Safety Follow-up Visit for subjects who do not have the dose of VX-121 tablet in the fed state and with milk and have a Safety Follow-up Visit, or (3) 7 days after the last dose of study drug for subjects who do not have the dose of VX-121 tablet in the fed state and with milk, and do not have a Safety Follow-up Visit.
- **TE Period 3 (tablet [fed and with milk])** will begin from the administration of VX-121 tablet in fed state and with milk through the Safety Follow-up Visit or 7 days after the last dose of study drug for subjects who do not have a Safety Follow-up Visit..

For subjects participating in Part D, the **TE Period** will be from first dose date of study drug to Safety Follow-up Visit for subjects who have a safety follow-up visit; or 28 days after the last dose date of study drug for subjects who do not have a safety follow-up visit.

Treatment Groups

The Treatment Groups in Part A (excluding Cohorts A3 and A9), B, C and D will be defined as the corresponding VX-121 dose groups.

The 2 Treatment Groups in Cohort A3 will correspond to suspension [fed] and suspension [fed and with milk] respectively.

The 3 Treatment Groups in Cohort A9 will correspond to suspension [fed], tablet [fed] and tablet [fed and with milk] respectively.

Baseline value

The baseline value will be defined as the most recent non-missing measurement (scheduled or unscheduled) collected before the first dose of study drug. If a pre-dose measurement is missing and no drug-free unscheduled assessments are performed before the first dose of the study, the baseline will be missing. For ECG, the baseline value will be defined as the most recent non-missing measurement (or the average of triplicate measurements, if the most recent non-missing measurements are obtained in triplicate), before the first dose of study drug of the Treatment Period.

Absolute change from baseline will be calculated as post-baseline value – baseline value.

Relative change from baseline will be calculated as (post-baseline value – baseline value)/baseline value.

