9.4.2 Clinical Laboratory Assessments

All statistical analyses of laboratory values will be performed using SI units. Continuous hematology, clinical chemistry and coagulation (Part D only) results including baseline and change from baseline values will be summarized at each scheduled time point by treatment group/treatment sequence for each part using descriptive statistics.

For Part D, the number and percentage of subjects meeting at least 1 threshold analysis criterion event, during the TE period for Treatment Period, will be summarized by treatment group. The threshold analysis criteria are provided in [Appendix D](#).

Clinically significant abnormal laboratory findings will be reported as AEs.

9.4.3 [Electrocardiogram](#)

A summary of raw values and change from baseline values will be provided for each scheduled time point by treatment group/treatment sequence for each part during the TE Period for the following 12-lead ECG measurements using descriptive statistics: RR interval, PR interval, QT interval, QTcF interval, QRS duration, and Heart Rate (beats per minute).

For Part D, the number and percentage of subjects meeting at least 1 threshold analysis criterion during the TE period for the Treatment Period will be summarized by treatment group. The threshold analysis criteria are provided in [Appendix D](#).

In addition, the number and percentage of subjects by maximum value of QT/QTc intervals during the TE period, categorized as ≤ 450 msec, >450 msec and ≤ 480 msec, >480 msec and ≤ 500 msec, and >500 msec, as well as maximum change from baseline value of QT/QTc intervals during the TE period, categorized as ≤ 0 msec, >0 msec and ≤ 30 msec, >30 msec and ≤ 60 msec, and >60 msec will be tabulated based on scheduled and unscheduled 12-lead ECG measurements by treatment group/treatment sequence for each part.

Clinically significant abnormal findings will be reported as AEs.

9.4.4 [Vital Signs](#)

A summary of raw values and change from baseline values will be provided for each scheduled time point by treatment group/treatment sequence for each part using descriptive statistics for the following vital signs measurements: BMI (kg/m^2), weight (kg), height (cm), systolic and diastolic blood pressure (mm Hg), body temperature ($^{\circ}\text{C}$), pulse rate (beats per minute), and respiratory rate (breaths per minute).

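### Cohorts A3 and A9 report ECG and vital-sign changes by period treatment but measure them all from one baseline before the first dose; a period baseline should be added alongside

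*SAP*

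**What the plan says.** SAP 9.1 defines the general baseline as follows: "The baseline value will be defined as the most recent non-missing measurement (scheduled or unscheduled) collected before the first dose of study drug". For ECG it uses the same anchor, with triplicates averaged, and places it "before the first dose of study drug of the Treatment Period". Protocol 12.3.4 agrees for safety variables: "the baseline value will be defined as the most recent non-missing measurement collected before the initial administration of study drug". Protocol 9.1.1.2 describes the Treatment Period in Parts A to C as one stay, in which subjects "will remain in the clinical research unit (CRU) for the duration of the Treatment Period". Together these point to a single baseline per subject.

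SAP 9.1 also splits A3 into 2 and A9 into 3 treatment-emergent periods and makes each a treatment group: "The 3 Treatment Groups in Cohort A9 will correspond to suspension [fed], tablet [fed] and tablet [fed and with milk] respectively". SAP 9.4.3 and 9.4.4 tabulate ECG and vital-sign changes by treatment group or sequence. SAP 9.4.3 adds categories for the "maximum change from baseline value of QT/QTc intervals during the TE period". The SAP gives period-specific rules for concomitant medications (9.2.4) and adverse events (9.4.1), but none for baseline.

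Predose ECGs are scheduled in every period. For A9 (Protocol Table 3-4): "On Days 1, 9, and 17, ECGs will be collected before dosing". For A3 (Protocol Table 3-3): "On Days 1 and 9, ECGs will be collected before dosing". Vital signs on dosing days are also taken before dosing.

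**The concern.** In A9 the suspension's postdose ECGs on Day 1 are compared with a value from the same morning. The tablet-with-milk ECGs on Day 17 are compared with a value 16 days older, taken before two other VX-121 doses. In A3 the milk period's reference is 8 days older and precedes a dose of placebo or VX-121.

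The design does not separate the time effect from the treatment effect. A9 is open-label with a single sequence, so period and treatment are confounded. In A3 every subject receives open-label VX-121 on Day 9, so the milk period has no concurrent placebo. Any difference between days is read as part of the later treatment's change.

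Each earlier period also runs until the next dose. The Day 9 predose ECG, and in A9 the Day 17 predose ECG, therefore counts toward the maximum of the treatment before it.

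ECGs and vital signs are named in the primary endpoint, and with about 8 subjects one chance case above 30 ms reads as 12.5%. For vital signs, which are taken daily in every period, the issue is elapsed time rather than the loss of a same-day reference.

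**Working it through.** The plan states no figure on this point, so there is none to reproduce.

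**Inputs from the documents.** About 8 subjects in A9. The A9 ECG schedule (Table 3-4) has a predose tracing and tracings at 1, 3, 5 and 6 hours on Days 1, 9 and 17, and one at follow-up. Under the SAP period definitions, Periods 1 and 2 each hold 4 postdose ECGs plus the next period's predose ECG, and Period 3 holds 4 postdose ECGs plus follow-up. That is 5 per period, so the number of chances is equal.

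**Assumptions (the documents give none).** QTc equals a day effect (SD sb) plus within-day error (SD sw) plus linear drift, with no drug effect. Main case sw = 8 ms; sb 0 to 10 ms; drift 0 or ±0.3 ms per day.

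**SD of one postdose change.**
- Same-day reference: √2 × sw = √2 × 8 = 11.3 ms.
- Reference from another day: √(2 × (sw² + sb²)) = √(2 × (64 + 64)) = 16.0 ms at sb = 8.

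**Chance that the maximum change exceeds 30 ms in A9, by simulation (sw = 8, no drift).**

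| sb (ms) | Single baseline: Period 1 | Single baseline: Periods 2 and 3 | Period baseline, same 5 ECGs: every period |
|---|---|---|---|
| 0 | 1.7% | 1.7% | 1.7% |
| 5 | 2.5% | 4.5% | 2.5% |
| 8 | 4.2% | 9.2% | 4.2% |
| 10 | 6.0% | 13% | 6.0% |

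With a period baseline and only the 4 same-day postdose ECGs, the rate is about 1.4% in every period, whatever sb is.

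**Expected subjects above 30 ms at sb = 8.** 8 × 0.042 = 0.34 in Period 1 and 8 × 0.092 = 0.74 in each later period, a difference of 0.40.

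**Drift (sw = 8, sb = 5, single baseline).** The mean postdose change is the drift rate times the days elapsed: 0.3 × 8 = 2.4 ms and 0.3 × 16 = 4.8 ms.

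| Drift (ms/day) | Mean change, Periods 1/2/3 (ms) | Maximum change above 30 ms, Periods 1/2/3 |
|---|---|---|
| +0.3 | 0 / +2.4 / +4.8 | 3.2% / 7.5% / 10.8% |
| −0.3 | 0 / −2.4 / −4.8 | 2.1% / 2.6% / 1.6% |

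With a period baseline the mean postdose change is 0 in every period under either drift.

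This model fits the A9 schedule only. A3 Period 2 ends at follow-up or 7 days after the last dose, whichever comes first, so its count of ECGs can differ.

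**The case against.** The strongest defence is that a single drug-free reference is a sound choice for safety. It cannot be contaminated by residual drug, whereas a Day 9 or Day 17 value could be, and a period baseline read alone could hide a persisting effect. This stands, and it is why the existing tables should stay.

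The practical stakes are also modest. Safety is descriptive with no hypothesis tests, and the tablet and milk objectives concern PK and bioavailability. Raw values are summarised at each time point, the absolute QT/QTc categories need no baseline, and all subject data are listed. A3 is shown by sequence, so the placebo-first and VX-121-first subjects can be told apart. In all the assumed scenarios, changes above 60 ms stay at or below about 0.5%. All of this limits the size of the point but does not remove the mixing of time and treatment in the change tables.

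A reader might infer more than the documents support:

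- **That later periods must show more threshold crossings by construction.** They need not. Extra crossings require between-day variance or upward drift, and downward drift can push Period 3 below Period 1. Nor is Period 1 free of drift, since it includes the Day 9 predose ECG.
- **That every safety change uses a Day 1 value.** In A9, chemistry and hematology are scheduled on Days −1, 2, 10 and 18 and at follow-up, so their scheduled baseline is Day −1.
- **That the 21-day gap between cohorts shows 8 days to be too short.** Protocol 9.3.1 applies that gap to subjects joining another cohort, and judges the A9 interval adequate on preliminary clinical data.
- **That a period baseline alone cuts the rate from 9.2% to 1.4%.** Like for like it goes from 9.2% to 4.2%. The rest comes from dropping the fifth ECG.

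**Conclusion.** The point holds as a cheap improvement, not as an error in the plan. For A3 and A9, one pre-first-dose baseline combined with reporting by period treatment puts between-day variation and drift into the later treatment's ECG and vital-sign changes. The bias has no predictable direction: it could suggest a tablet or milk effect, or mask one.

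In A9, at assumed SDs of 8 ms within and between days, the excess is about 0.4 of 8 subjects per later period. It is zero if between-day SD is zero, and the rates are about 6% against 13% at a between-day SD of 10 ms. These sizes rest on SDs that the documents do not supply. The structural point rests on the text alone.

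There is slight ambiguity in the wording. Protocol 9.6.1 speaks of each Treatment Period and, for all dosing occasions, of baseline vital signs and ECGs before study drug. Protocol 9.1.1.2 and 12.3.4 favour a single baseline, but the SAP should say so outright for these cohorts.

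**What to change.** In SAP 9.1, for ECG and vital signs in Cohorts A3 and A9 only:

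1. Add a period baseline: the last non-missing value before that period's dose (Days 1 and 9 in A3; Days 1, 9 and 17 in A9). State what happens if the dosing-day value is missing, because in A9 the previous scheduled ECG is a postdose tracing from the earlier treatment.
2. From it, report change from baseline and the maximum QT/QTc change categories by treatment.
3. Leave the next period's predose ECG out of the preceding treatment's maximum.
4. Keep the tables from the drug-free pre-first-dose baseline alongside, so that any residual effect stays visible. State that the two sets are to be read together.

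Leave laboratory tests as they are: A9 has no Day 9 or Day 17 predose sample.

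The cost is a few lines of SAP text and one extra set of descriptive tables for two cohorts of about 8. The ECGs and vital signs are already scheduled.

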9.2 Background Characteristics

9.2.1 Subject Disposition

Disposition summary will be based on the All Subjects Set.

The number and percentage of subjects in the following disposition categories will be summarized by treatment group/treatment sequence and overall for each part:

- Randomized
- Safety Set
- Full Analysis Set

The number and percentage (based on Safety Set) of subjects in each of the following disposition categories will be summarized by treatment group/treatment sequence and overall, when applicable:

- Completed study drug treatment
- Prematurely discontinued treatment and the reason for discontinuation
- Completed study
- Prematurely discontinued the study and the reason for discontinuation

9.2.2 Demographics and Baseline Characteristics

Demographics and baseline characteristics summary will be based on the Safety Set.

Demographics and baseline characteristics (age, sex, race, ethnicity, weight, height, body mass index (BMI) and etc.) will be summarized overall and by treatment group for Parts A (Cohorts A1, A2 and A4 through A6, or A7, A8 when applicable), B, C, and D and by treatment sequence for Cohorts A3 and A9.

No statistical tests will be done to evaluate baseline imbalances between groups.

9.2.3 Medical History

Medical history will be coded by using the Medical Dictionary for Regulatory Activities (MedDRA). For the Safety Set, medical history will be summarized descriptively by system

organ class and preferred term and by treatment group/treatment sequence and overall for each part. The corresponding data listing will also be provided.

9.2.4 Prior and Concomitant Medications

Medications will be coded using the World Health Organization-Drug Dictionary (WHO-DD) September 2017, Format B2 or higher. Medications used in the study will be categorized as prior and/or concomitant medications as follows:

1. **Prior medication:** Medication that started before the first dose of study drug, regardless of when dosing of the medication ended
2. **Concomitant medication:** Medication received at or after the first dose of study drug, medication that was received before initial dosing and continued after initial dosing of study drug, or medication with missing stop date

If a medication start date is on or after the date of initial dosing of the study drug, then the medication will be summarized as concomitant medication regardless of whether the medication end date is missing or not. If a medication end date is before the date of initial dosing of the study drug, then the medication will be summarized as prior medication regardless of whether the medication start date is missing or not. Note that medication that started before initial dosing of the study drug and continued after initial dosing will be summarized as prior medication and separately as concomitant medication.

Missing or partial dates will be imputed for medication. Algorithm for missing or partial start date is:

- Missing day: first day of the month is imputed;
- Missing month: January is imputed;
- Missing year: not imputed.

Algorithm for missing or partial end date is:

- Missing day: last day of the month is imputed;
- Missing month: December is imputed (31 December if day is also missing);
- Missing year: not imputed.

Missing data algorithms will be reviewed to ensure the algorithms work. For example, end date will not be before the start date after the imputation.

For Cohorts A3 and A9, concomitant medications will be assigned to each TE period based on the start date of the medication and the study drug administration dates (concomitant medications taken during the TE period will be assigned to the TE period, and so forth).

Note that a concomitant medication may be assigned to multiple TE periods.

Prior medications will not be summarized, but will only be listed based on All Subjects Set. Concomitant medications will be summarized using preferred name by treatment group/treatment sequence and overall for each part. Concomitant Medications summary will be based on the Safety Set.

Prior and concomitant non-drug therapy will also be listed based on All Subjects Set.

9.2.5 Study Drug Exposure and Compliance

Study drug exposure in Parts B, C and D (i.e., duration of treatment) will be summarized by treatment group and overall for the Safety Set.

Study drug exposure (in days) will be defined as (last date of dosing – first date of dosing) + 1.

The study drug administration will be presented in an individual subject listing.

Compliance analysis will be provided for Part D only based on the FAS, and will be presented by treatment group and overall. Study drug compliance will be calculated as: $100 \times [1 - (\text{total number of days of study drug interruption}) / (\text{duration of study drug exposure in days})]$. A study drug interruption on a given day is defined as an interruption of any study drugs on that day. Study drug compliance will be summarized descriptively by the number of subjects (n), mean, SD, median, min, and max. It will also be summarized in categories: <80% and $\geq 80\%$ using frequency tables.

In addition, percentage of tablets taken will be calculated using the following formula: $100 \times [(\text{total number of tablets dispensed for the Treatment Period}) - (\text{total number of tablets returned})] / (\text{total number of tablets planned to be taken per day} \times \text{duration of study drug exposure in days})$. Summary similar to the study drug compliance will be produced based on the FAS for Part D only.

